**Table 9** **EMR clinical characteristics in matched dabigatran and warfarin initiators**

EMR clinical characteristic	Dabigatran initiators	Warfarin initiators
	N=	N=
[REDACTED]		
Smoking		
Alcohol consumption		
Obesity		
...		

[figure not shown]
Note: anticoagulant initiation [REDACTED] are based on claims data

We will seek to define variables derived from the EMR in a manner that reduces missingness. Accordingly, most variables will be defined as presence or non-presence in the EMR, which we will take as a proxy of being medically-recognized. For example, if smoking is noted in the medical record, it will be recorded as present, if it is not present, it will be assumed that the patient does not smoke. We will also evaluate the patterns of missing data in the EMR clinical characteristics.

Objective 2: Prediction Rule

[figure not shown]
Within the EMR linked subpopulation, a prediction model will be developed [REDACTED] with particular focus on covariates that are found to represent potentially important unmeasured confounding in the primary analysis. Specifically, a logistic regression model (potentially a multinomial logistic regression, depending on the number of categories for the EMR characteristic) will be estimated [REDACTED] that uses the EMR covariate as the model outcome and all available claims-based covariates as predictors. [REDACTED]

For [REDACTED] continuous EMR-based characteristic, a linear regression model will be estimated. Coefficients from these models will be reported as well as prediction accuracy, defined by the R2 statistic.

*Objective 3: Potential Unmeasured Confounding Assessment*

To assess the potential for confounding, we will conduct a series of logistic regression analyses that predict exposure (dabigatran versus warfarin) from covariates.

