#### 9.3.2 Outcomes

EMR-based clinical characteristics that are typically used as covariates will be treated as outcomes in this validation study. Unless otherwise noted, all of these outcomes will have an indicator for being recorded in EMR (Present, Y/N). Index date is the date of dabigatran or

warfarin initiation. All characteristics will be assessed prior and including the medication initiation date (index date). The characteristics presented in [Table 1](#) reflect likely availability in the EMR.

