**Table 1 Outcome definitions**

Outcome	Definition	Present	Categories if present
Primary			
Obesity	Calculated BMI >30 or recorded "obesity"	Y/N	Obese, not-obese based on note of obesity or recorded BMI>30.
Smoking	Any note on smoking	Y/N	Current & past combined and nonsmoker & not noted combined.
Alcohol consumption	Any note on alcohol use	Y/N	Alcohol use (any); No use
Abnormal renal function	Any note of: Dialysis, renal transplant Serum Creatinine >1.3 mg/dL	Y/N	
Bleeding history or predisposition	Any note of: Major bleeding requiring hospitalization or blood transfusion or causing a decrease in hemoglobin level of > 2 g/L	Y/N	
Renal function	Estimated GFR closest to index dispensing	Y/N	The value
Serum Creatinine	Closest to the index date	Y/N	The value
Abnormal liver function	Any note of: Liver disease, cirrhosis, Active hepatitis C Active hepatitis B Active hepatitis A AST/ALT >3X upper limit of normal Absence of any note would be considered as absence of the disease	Y/N	

[figure not shown]
Table 1 (cont'd) Outcome definitions

[figure not shown]
Outcome	Definition	Present	Categories if present
Secondary			
Duration of atrial fibrillation	Years/months prior to initiation of dabigatran/warfarin	Y/N	Number of months prior to index date for the earliest note
History of adherence	Any note of patient adherence/lack thereof in EMR	Y/N	Non-adherent Adherent
History/duration of hypertension	Any note of: Hypertension SBP >120 mmHg Hypertension drugs	Y/N	Number of months prior to index date for the earliest date
Uncontrolled Hypertension (for HASBLED)	SBP >160 mmHg using the most recent information prior to index date	Y/N	
History/duration of CHF	Any note of: CHF	Y/N	Number of months prior to index date for the earliest note
Prior TIA	Any note of TIA	Y/N	Also, number of months prior to index date if noted
Diabetes	Any note of: Diabetes Absence of any note of diabetes will be considered as absence of the disease	Y/N	
Hyperlipidemia	Any note of; Hyperlipidemia, dyslipidemia, LDL>130 mg/dl		
HAS Bled Score	As recorded (if recorded) or calculated from EMR data. [REDACTED]	Recorded/ calculated /none	The value
Use of antiplatelets or NSAIDs (needed for HASBLED)	Use of aspirin, clopidogrel, prasugrel, ticagrelor or NSADs (within 1 month or on the index date)	Y/N	
INR	Closest to the index date	Y/N	The value

[figure not shown]

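### No note is coded as no condition for smoking, liver disease, diabetes and most binary EMR items, while the visible text requires no EMR record on or before the index date

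*Combined protocol and SAP*

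**What the plan says.** **Coding.** Section 9.7.1, under Objective 1, states the general rule: "most variables will be defined as presence or non-presence in the EMR, which we will take as a proxy of being medically-recognized". Smoking is its worked example: "if it is not present, it will be assumed that the patient does not smoke". Table 1 agrees, giving the smoking categories as "Current & past combined and nonsmoker & not noted combined". For abnormal liver function Table 1 says "Absence of any note would be considered as absence of the disease", and for diabetes "Absence of any note of diabetes will be considered as absence of the disease".

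**Entry and time window.** The abstract and section 9.11.2 admit a matched patient to the linked subset if EMR data are available, with no condition on date or encounters. Section 9.3.2 reads every characteristic up to and including the index date. The 12-month rule in 9.11.1 is defined by enrollment and disenrollment dates.

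**What the plan already does about missing EMR data.** Section 9.3.2 gives outcomes a recorded-in-EMR indicator unless otherwise noted. Section 9.7.1 adds: "We will also evaluate the patterns of missing data in the EMR clinical characteristics". The abstract plans to describe, by drug, how each EMR characteristic appears in claims. Section 9.9 concedes that some EMR data will be missing. For some items Table 1 keeps recording apart from status. Adherence is defined as "Any note of patient adherence/lack thereof in EMR" and then split into adherent and non-adherent, alcohol has use and no-use levels once a note is present, and laboratory values carry an indicator plus the value.

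**The concern.** Differences between dabigatran and warfarin initiators in EMR items are the main result of this study. Objective 1 treats unbalanced items as potential unmeasured confounders, and Objective 3 regresses drug choice on covariates. When an item is coded absent because nobody wrote it down, or because the patient's EMR starts after the index date, its observed prevalence mixes patient status with chart depth.

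If chart depth is the same in both groups, prevalence is understated and comparisons change little. If it differs, Table 9 could show an imbalance that is not there or hide one that is. Hiding is the more serious error, because it would falsely reassure the claims-based safety studies that this study is meant to support.

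The planned checks would not reveal this. The representativeness and balance checks in 9.7.1 and 9.11.2 use claims covariates and the propensity score, neither of which measures EMR depth. The recorded indicator cannot help where yes/no is itself the disease status, as for liver disease or diabetes, because a no covers both not assessed and absent. The claims comparison can help for diabetes. It is weaker for smoking, which section 7 lists among confounders that claims may not capture sufficiently.

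**Working it through.** **Sample size, from the plan.** Section 9.5: 20,000 × 5.5% = 1,100 per group, which reproduces the stated figure. The abstract's cohort of 15,000 per group gives 15,000 × 5.5% = 825. Both are carried below.

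**How a patient without pre-index EMR is handled.**
1. Section 9.11.2 admits the patient, because EMR data exist.
2. Section 9.11.1 does not remove the patient, because its 12-month rule is met by insurance enrollment.
3. Section 9.3.2 looks up to the index date and finds nothing.
4. Table 1 and 9.7.1 then code non-smoker, no liver disease and no diabetes.

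**Size.** True prevalence is taken from the 10% to 20% range that section 9.5 calls plausible for a confounder. The documents give no recording rates, so those below are assumptions.

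Observed prevalence = true prevalence × recording probability. The odds ratio (OR) comes from the observed proportions a and b, with

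SE(log OR) = √[1/(na) + 1/(n(1−a)) + 1/(nb) + 1/(n(1−b))] and 95% CI = OR × exp(±1.96 SE).

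*Equal true prevalence in both groups (false imbalance):*

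| True | Recorded | Observed | OR | 95% CI, n=825 | 95% CI, n=1,100 |
|---|---|---|---|---|---|
| 20% | 90% vs 85% | 18% vs 17% | 1.07 | 0.83-1.38 | 0.86-1.34 |
| 20% | 90% vs 80% | 18% vs 16% | 1.15 | 0.89-1.49 | 0.92-1.44 |
| 20% | 80% vs 60% | 16% vs 12% | 1.40 | 1.06-1.85 | 1.10-1.78 |
| 10% | 90% vs 85% | 9% vs 8.5% | 1.06 | 0.76-1.50 | 0.79-1.43 |
| 10% | 90% vs 80% | 9% vs 8% | 1.14 | 0.80-1.61 | 0.84-1.54 |
| 10% | 80% vs 60% | 8% vs 6% | 1.36 | 0.93-2.00 | 0.98-1.90 |

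Example for the third row at n=825: SE = √(1/132 + 1/693 + 1/99 + 1/726) = 0.1432.

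*True prevalence 20% vs 15% (hidden imbalance).* With full recording the OR is 1.42 (1.10-1.83 at n=825).

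| Recorded | Observed | OR | 95% CI, n=825 | 95% CI, n=1,100 |
|---|---|---|---|---|
| 85% vs 90% | 17% vs 13.5% | 1.31 | 1.00-1.72 | 1.04-1.66 |
| 80% vs 90% | 16% vs 13.5% | 1.22 | 0.93-1.60 | 0.96-1.55 |
| 60% vs 80% | 12% vs 12% | 1.00 | 0.74-1.35 | 0.77-1.29 |
| 60% vs 60% | 12% vs 9% | 1.38 | 1.00-1.89 | 1.05-1.82 |

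Patients without pre-index EMR enter the same formula. If a share f has none and the rest are fully recorded, the recording probability is 1 − f. With f of 10% in one group and 20% in the other, the result is the 90% vs 80% row.

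**The case against.** **The harm is hypothetical.** The documents give no recording rate and no reason why charting before initiation should differ by drug. Matching on calendar quarter and on a claims-based propensity score makes a large gap less likely. Equal under-recording barely moves the OR (1.38 against 1.42 at 60% recording). For false imbalance, only the widest assumed gap at 20% prevalence gives an interval that excludes 1. All of this stands and limits the weight of the point. It does not remove the masking risk, where a 10-point gap is enough to bring the interval across 1.

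**The coding is a disclosed choice.** The plan adopts it to reduce missingness and says that it measures medical recognition, not true status. Section 9.9 also says that some variation in assessment cannot be studied within scope. That defends the main coding, which need not change. It does not cover a patient with no chart to read before the index date.

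**Table 1 already separates some items.** This is right for alcohol, adherence and the laboratory values, which are not part of the point.

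**The missing-data evaluation is naturally read as by drug.** Objective 1 describes the two initiator groups, and Table 9 has one column for each. That reading is reasonable, so what remains there is a matter of wording.

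**The encounter rule may be in text that cannot be seen.** Figure 1 is not shown, and parts of Objective 1 and Table 9 are redacted. This stands: the point covers the visible text only.

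A reader might also infer that the plan ignores missing EMR data, or that the drug comparison is already shown to be biased. The documents support neither. The plan has an indicator, a planned evaluation and a stated limitation, and nothing shows that recording differs between the groups.

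**Conclusion.** The point holds in limited form. In the visible text, a linked patient with no EMR record on or before the index date would be counted as free of smoking, liver disease, diabetes and most other presence/non-presence items. That is misclassification by rule, and it understates prevalence to the extent that such patients exist. The documents do not say how many there are.

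An effect on the drug comparison also needs EMR depth or recording to differ between groups, which the documents neither show nor rule out. Under assumed gaps of 5 to 10 points, a false imbalance is small (OR 1.06 to 1.15) and within sampling error. Under the same gaps, a true OR of 1.42 shrinks to between 1.31 and 1.22. Only an assumed gap of 20 points produces a false OR near 1.4 or erases a true one of that size.

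This is a cheap improvement to the plan, with medium confidence.

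**What to change.** 1. In 9.11.2, require at least one EMR encounter on or before the index date, with the look-back window chosen by the sponsor. Alternatively, keep all linked patients and repeat the Objective 1 and 3 balance analyses in that subset as a sensitivity analysis. Either way, report by exposure group the number without pre-index EMR, the number of pre-index encounters and the length of look-back. If Figure 1 already contains such a rule, repeat it in the text.
2. For smoking, and for obesity where neither a BMI nor an obesity note exists, keep the current coding as the main analysis. Add a sensitivity analysis coded yes, documented no, and not recorded.
3. State that the planned missing-data evaluation and the recorded indicators are reported by exposure group.

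**Cost.** Some wording in 9.11.2 and 9.7.1, a few table rows, and sensitivity analyses on EMR data already being extracted. Restriction loses some precision. The 95% half-width of a difference at 20% prevalence is 1.96 × √(2 × 0.2 × 0.8 / n). If 10% to 20% of linked patients were removed (assumed), it rises from 3.9 points at 825 per group to 4.1 (n=742.5) or 4.3 (n=660). From 3.3 points at 1,100 per group it rises to 3.5 (n=990) or 3.7 (n=880).

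An encounter rule does not remove all under-recording. Results among recorded patients condition on charting, so they should remain sensitivity analyses. For items where yes/no is the disease status, no recorded-only analysis is possible, and the comparison of EMR depth has to serve instead.

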**Protocol for non-interventional studies based on existing data:**

Document Number:	c12696196-01
BI Study Number:	1160.219
BI Investigational Product(s):	PRADAXA (dabigatran)
Title:	Validation of predictors for oral anticoagulant medication choice using EMR data (Phase 3b of the BI/BWH Pradaxa study program)
Protocol version identifier:	1.0
Date of last version of protocol:	02 November 2016
PASS:	No
EU PAS register number:	Not available yet
Active substance:	Dabigatran etexilate
Medicinal product:	Pradaxa
Product reference:	EU/1/08/442/001-019
Procedure number:	EMEA/H/C/000829
Joint PASS:	Not applicable
Research question and objectives:	
The research question is whether select patient characteristics that may be incompletely captured by insurance claims data, differ between dabigatran and warfarin initiators.
 
Objectives:
 
 
1) Descriptive: To identify select clinical covariates from electronic medical records that might be associated with initiation of oral anticoagulant medications (dabigatran or warfarin) in NVAF patients at risk for stroke and are not usually well captured in the associated claims database
 
2) Prediction Rule: To assess how well EMR-based clinical characteristics can be captured on the basis of claims data only
 
3) Assess Balance: To assess the potential for unmeasured confounding in dabigatran vs warfarin comparative effectiveness and safety studies based on administrative claims
 

Proprietary confidential information © 2016 Boehringer Ingelheim International GmbH or one or more of its affiliated companies

	databases
Country(-ies) of study:	US
Author:	
Marketing authorisation holder(s):	Boehringer Ingelheim
MAH contact person:	
Date:	02 November 2016
Page 2 of 55	
Proprietary confidential information © 2016 Boehringer Ingelheim International GmbH or one or more of its affiliated companies. All rights reserved. This document may not - in full or in part - be passed on, reproduced, published or otherwise used without prior written permission	

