Variables:	
Patient characteristics derived from insurance claims (claims-based covariates)
 
This study will characterize patients initiating oral anticoagulant medications with respect to select characteristics, some of which might be reflected differently in claims data compared to electronic medical records prior to and including the date of initiation. These characteristics from EMR data are usually treated as covariates but will be considered outcomes in this validation study.
 
These characteristics include:
 
Primary Outcomes
 
 
• Obesity
 
• Smoking
 
• Alcohol consumption
 
• Abnormal renal function
 
• Bleeding history or predisposition
 
• Renal function (estimated GFR)
 
• Serum Creatinine
 
• Abnormal liver function
 
 
Secondary Outcomes
 
 
• Duration of atrial fibrillation
 
• History of adherence
 
• History/duration of hypertension
 
• Uncontrolled Hypertension (for HAS-BLED)
 
• History/duration of CHF
 
• Prior TIA
 
• Diabetes
 
• Hyperlipidemia
 
		

Name of company: Boehringer Ingelheim			
Name of finished medicinal product: Pradaxa® (Dabigatran etexilate), or warfarin			
Name of active ingredient: Dabigatran etexilate or warfarin			
Protocol date: 02 November 2016	Study number: 1160.219	Version/Revision: 1.0	Version/Revision date:
Variables:	
 
HAS-BLED Score
 
Use of antiplatelets or NSAIDs (needed for HAS-BLED)
 
		
Data sources:	This study will be conducted within MarketScan data linked to electronic medical records.		
Study size:	
Study cohort: approximately 15,000 dabigatran initiators PS-matched to 15,000 warfarin initiators
 
EMR-linked subset: approx. 5.5% of the study cohort.
		

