Data analysis:	
 
Analyses will describe the presence in the claims data of each EMR-based clinical characteristic among initiators of dabigatran and initiators of warfarin.
 
A prediction algorithm to identify in the claims data each of the EMR-based clinical characteristic will be developed. The prediction algorithm will be estimated using a regression model that uses each of the EMR characteristic as the model outcome and all available claims-based covariates as predictors.
 
Strength of association between each EMR-based covariate and medication choice will guide quantitative assessments of potential confounding of the association between anticoagulant and clinical outcomes.
 
		
Milestones:	
Draft Protocol: September 2013
 
Final Protocol: November 2016
 
Draft Report: July 2017
 
Final Report: September 2017
		

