## **8. RESEARCH QUESTION AND OBJECTIVES**

The objectives of this study are:

- 1) **Descriptive:** To identify select clinical covariates from electronic medical records that might be associated with initiation of oral anticoagulant medications (dabigatran or warfarin) in patients with NVAF at risk for stroke and are not usually well captured in the associated claims database.
- 2) **Prediction Rule:** To quantify the association between EMR-based clinical characteristics and patterns of insurance claims
- 3) **Assess Balance:** To assess the potential for unmeasured confounding in dabigatran vs warfarin comparative effectiveness and safety studies based on administrative claims databases

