## **9.5 STUDY SIZE**

[figure not shown]
This study will identify covariates that represent potential confounding variables among dabigatran and warfarin users within a sampled population. The ability to identify a covariate and the precision for estimating potential confounding from the covariate will depend on the numbers of patients from whom electronic medical record data is extracted, and features of the covariate itself, such as how certain it is to be recorded in the medical record and whether binary (yes/no) or other.

The PS-matched dabigatran and warfarin initiators during Oct 2010– December 2013 period are approximately 20,000 each. Assuming that 5.5% of this study group will be linked to EMR, the EMR-linked subset up to Dec 2013 will consist of approximately 1100 patients in each exposure group.

The precision of estimated prevalence for a covariate obtained from the EMR depends on the prevalence of the covariate, and the sample size. With 10,000 dabigatran initiators, this study will estimate a patient characteristic that has a 10% prevalence with considerable precision (the 95% confidence interval will be 9.4% to 10.6%) ([Table 7](#)). A characteristic not captured in claims, but present in the medical record with a prevalence of 10% to 20% is plausibly a confounding variable and so this table enumerates characteristics with these prevalences. The table has not been extended below 10% since such lower prevalence characteristics have progressively less ability to produce meaningful confounding, so that while the study will have less precision to estimate such a characteristic, validation of the presence for such a low prevalence characteristic becomes unnecessary. At the other end of the range presented in the table, a characteristic with a prevalence above 20% will be identified with even greater precision, so that it also does not need to be depicted in the table.

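### Objective 2 reports what appears to be an in-sample R2 as prediction accuracy for continuous EMR characteristics, which reads too high; unless redacted text already validates it, report a corrected R2 and keep the coefficients

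*Combined protocol and SAP*

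**What the plan says.** Section 9.7.1, Objective 2, develops its models within the EMR-linked subset. Continuous characteristics get a linear regression, and the reporting rule is: "Coefficients from these models will be reported as well as prediction accuracy, defined by the R2 statistic". The abstract (Data analysis) describes a regression model that "uses each of the EMR characteristic as the model outcome and all available claims-based covariates as predictors".

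The aim is worded in two ways. The title page has "To assess how well EMR-based clinical characteristics can be captured on the basis of claims data only", which is a prediction aim. Section 8 (and the abstract) has "To quantify the association between EMR-based clinical characteristics and patterns of insurance claims", which is an association aim.

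Most characteristics are binary: section 9.7.1 says that "most variables will be defined as presence or non-presence in the EMR". Table 1 keeps some as a value or a number of months: eGFR ("Estimated GFR closest to index dispensing"), serum creatinine, INR, the HAS-BLED score and the durations. The first two are among the eight primary outcomes.

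On sample size, the abstract gives "EMR-linked subset: approx. 5.5% of the study cohort", with about 15,000 matched initiators per group. Section 9.5 says "the EMR-linked subset up to Dec 2013 will consist of approximately 1100 patients in each exposure group".

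**The concern.** A least-squares model fits some of the noise in the data it was estimated from, so R2 computed in those data overstates the population value. It overstates performance in other patients by more. The title-page objective concerns other patients: those with claims but no linked record. R2 is the only readable accuracy measure for the continuous characteristics. An inflated R2 would make claims data look like a better proxy for, say, renal function than they are, in a study meant to show what claims miss.

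The excess also grows as the number of patients with a recorded value falls. R2 figures for laboratory tests with different recording rates are then not directly comparable. Section 9.9 accepts that some EMR data will be missing but gives no rates, so the importance of this is unknown.

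The logistic models are outside this point, because no accuracy measure for them is readable.

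**Working it through.** **Is validation named anywhere readable?** Section 9.7.1 names no adjusted R2, cross-validation, bootstrap or hold-out. Section 9.7.2 defines no further analysis. The validation analyst in section 9.8 checks programs, not model performance.

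**Sample size n**
- Section 9.5: 20,000 × 5.5% = 1,100 per group, which reproduces the plan's figure; 2 × 1,100 = 2,200.
- Abstract: 15,000 × 5.5% = 825 per group; 2 × 825 = 1,650.
- The 2,200 counts only October 2010 to December 2013 (39 months), while section 9.11.1 runs the cohort to December 2014 (51 months). Assuming constant accrual, 20,000 × 51/39 = 26,154 per group; × 5.5% × 2 = 2,877.
- Low case (assumed): half of 1,650 have a recorded value, n = 825.

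**Assumptions:** p = 30 or 100, since the count is not readable; true R2 of 10%, with 30% as a second case.

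**Formulas** (R2 = population value; the second assumes normal predictors)
- Expected in-sample R2 ≈ R2 + (1 − R2) × p/(n − 1)
- R2 in new patients ≈ 1 − (1 − R2) × (n + 1)(n − 2)/[n(n − p − 2)]

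Example, n = 1,650, p = 100, R2 = 10%: the excess is 0.90 × 100/1,649 = 5.5 points, so in-sample R2 is 15.5%. In new patients, 1 − 0.90 × (1,651 × 1,648)/(1,650 × 1,548) = 4.1%.

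**Results at true R2 of 10%**

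| n | p | In-sample R2 | Excess over true R2 (points) | R2 in new patients | Gap to new patients (points) |
|---|---|---|---|---|---|
| 1,650 | 30 | 11.6% | 1.6 | 8.3% | 3.4 |
| 1,650 | 100 | 15.5% | 5.5 | 4.1% | 11.3 |
| 2,200 | 30 | 11.2% | 1.2 | 8.7% | 2.5 |
| 2,200 | 100 | 14.1% | 4.1 | 5.7% | 8.4 |
| 2,877 | 30 | 10.9% | 0.9 | 9.0% | 1.9 |
| 2,877 | 100 | 13.1% | 3.1 | 6.7% | 6.4 |
| 825 | 30 | 13.3% | 3.3 | 6.5% | 6.8 |
| 825 | 100 | 20.9% | 10.9 | −2.6% | 23.5 |

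At a true R2 of 30%, the excess at n = 1,650, 2,200 and 2,877 is 1.3, 1.0 and 0.7 points (p = 30) or 4.2, 3.2 and 2.4 points (p = 100). With no association at all, n = 1,650 and p = 100 still give an expected in-sample R2 of 100/1,649 = 6.1%.

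**Do the corrections work?** Simulation with independent normal predictors and true R2 of 10%, 500 replicates per cell, at n = 1,650 and p = 30/60/100:

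| Measure | p = 30 | p = 60 | p = 100 |
|---|---|---|---|
| In-sample | 11.6% | 13.2% | 15.4% |
| Adjusted | 10.0% | 9.9% | 9.9% |
| New patients | 8.3% | 6.6% | 4.1% |
| 10-fold cross-validated | 8.0% | 6.0% | 3.3% |

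Against the new-patient value, cross-validation is low by 0.2/0.6/0.8 points and in-sample R2 is high by 3.4/6.6/11.3. At n = 2,200 the errors are 0.1/0.3/0.5 low and 2.6/5.1/8.5 high. At n = 825 they are 0.6/0.9/1.8 low and 6.7/13.8/23.4 high. Bootstrap optimism correction (300 replicates, 20 resamples) is high by 0.2/0.0 points at n = 1,650 (p = 30/60) and by 0.3/1.0/2.5 at n = 825. Adjusted R2 recovers the population value but still exceeds what new patients would show.

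**The case against.** The strongest objection is redaction. Objective 2 has blacked-out text after the sentence parts that introduce the model and its estimation, after the predictor list, and inside the phrase introducing continuous characteristics. A validation step could sit in any of these, and redacted content does not count as missing. This stands as a condition on the finding. The accuracy sentence itself carries no redaction, however, and refers to no validated version of R2.

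Second, p is unreadable. At p = 30 and the plan's own n, the excess over the true R2 is only 1.2 to 1.6 points; the large figures need p near 100 or many missing values. This also stands.

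Third, nothing readable commits the plan to linear models for INR, HAS-BLED or each duration. That is fair; eGFR and serum creatinine are the firm candidates.

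Fourth, no readable decision rule uses R2, the Objective 3 exposure models do not depend on it, and adjusted R2 would be enough under the section 8 wording. If no variable selection is used, a reader given all coefficients and the recording counts could compute adjusted R2 unaided. All true, but adjusted R2 does not answer the title-page question about prediction from claims alone.

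Fifth, cross-validation and bootstrap correction can disagree: at n = 825 and p = 100 they lie 1.8 points low and 2.5 points high, 4.3 points apart. They should therefore not be left as a choice after the data are seen. In-sample R2 is 23.4 points high in that cell, so either is far closer to the target.

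**Conclusion.** The concern holds as conditioned. Unless the redacted text provides internal validation, the stated accuracy measure for the linear models is an in-sample R2, and it answers the prediction aim too favourably. The direction is certain for least squares. The size depends on an unreadable p. At a true R2 of 10% and n = 1,650 to 2,200, the gap between the reported figure and performance in new patients is 2.5 to 3.4 points for p = 30 and 8.4 to 11.3 points for p = 100. It would be larger where values are often unrecorded and somewhat smaller if the extra year of accrual raises n.

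This is a worthwhile, cheap improvement to one reported figure. It does not threaten the main confounding assessment. Confidence is medium, because of the redactions and the unknown p.

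**What to change.** Keep the coefficients and replace the accuracy sentence in section 9.7.1 with wording such as:

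> Coefficients from these models will be reported. Prediction accuracy is the 10-fold cross-validated R2 (or the bootstrap optimism-corrected R2, chosen before analysis), with any model-building step repeated in each resample. Apparent and adjusted R2, the number of patients with a recorded value and the number of predictors are shown alongside.

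The final text should name one of the two corrections. Adjusted R2 then serves the association wording in section 8, and the corrected R2 serves the prediction wording on the title page and in the abstract's data analysis. If the redacted text already contains internal validation, it is enough to say here that R2 is the validated figure and to add n and p for each model.

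The cost is one sentence and slightly more computing, with no new data and no change to the planned models. The reported accuracy will be lower, and 10-fold cross-validation itself reads slightly low (0.2 to 0.8 points at n = 1,650 in the simulation).
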